## 10.4. Appendix 4: Data Display Standards & Handling Conventions

### 10.4.1. Study Treatment & Sub-group Display Descriptors

Study Treatment Descriptions		
Code	Description	Order of Table Presentation
1	Retosiban (Combined)	4
2	ZINN Atosiban	2
3	NEWBORN-1 Placebo	1
2, 3	Comparators (Combined)	3

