The Phase 3 program included 2 global blinded, randomized, controlled trials (200721 [ZINN] and 200719 [NEWBORN-1]) and a single infant follow-up trial (200722 [ARIOS]). Eligible subjects were aged 12 to 45 years with an uncomplicated singleton pregnancy and intact membranes in spontaneous preterm labor at 24^{0/7} to 33^{6/7} weeks' gestation. ZINN (N=330) aimed to show superiority of retosiban (IV) over atosiban on time to delivery (first subject first visit [FSFV] was March 2015). NEWBORN-1 (N=900) was designed to demonstrate neonatal benefit (based on a composite endpoint) as well as time to delivery or time to treatment failure over placebo (FSFV February 2016). The intervention trials were terminated early on 11 May 2017 because of slow recruitment and the retosiban project was discontinued permanently. Last subject last visit (LSLV) was 24 July 2017 for NEWBORN-1 and 25 August 2017 for ZINN. Meaningful analyses of these well-controlled trials could not be performed due to small numbers of completing participants. Mean time to delivery or treatment failure in the placebo-controlled trial was 18.9 days with retosiban (n=10) versus 11.1 days with placebo (n=13). Two neonates in the retosiban and 4 in the placebo group had ≥ 1 component of the neonatal composite endpoint. The adjusted mean time to delivery in the atosiban comparator trial was 32.51 days with retosiban (n=50) compared with 33.71 days with atosiban (n=47; $P>0.05$). Maternal, fetal, and neonatal AEs were no more common with retosiban than placebo or atosiban.

In NEWBORN-1, 1 participant in the retosiban group provided cord blood and breast milk samples; retosiban was found in both (cord blood, 1.9 μ g/L; breast milk, 3.6 μ g/L).

In ZINN, 12 women in the retosiban group provided cord blood samples, none of which had detectable levels of retosiban. One participant also provided a breast milk/colostrum sample. The retosiban concentration was 0.3 µg/L.

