8.3.3. Treatment Comparisons

8.3.3.1. Primary Comparisons of Interest

The primary treatment groups are retosiban, placebo, and atosiban.

The primary comparisons between these treatment groups will be:

- Retosiban versus placebo
- Retosiban versus atosiban

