Due to the early termination of 200719 and 200721, the sample size of ARIOS is small with a total of 98 babies enrolled (6 placebo treated subjects from NB-1, 43 atosiban treated subjects from ZINN and 49 retosiban treated subjects from NEWBORN-1 and ZINN). This represents just 8% of the planned 1230 infants that were to be enrolled in the study. The intent of the design of ARIOS was to compare data from the retosiban exposed group in each of the treatment trials to the placebo exposed group. In order to accomplish this, data from both 200719 and 200721 were to be pooled from all the babies exposed to retosiban and compared against placebo-exposed babies. As there were only 6 babies exposed to placebo with the drop-out rate expected to increase as the study progresses, the sample size will not be sufficient to permit a meaningful comparison of long-term safety between active treatment and placebo subjects if the follow-up study was continued for 5 years of follow-up.

On 28 August 2018, the retosiban IDMC, composed of 1 pediatrician, 2 neonatologists, 2 maternal-fetal medicine specialists and a statistician, confirmed that there were no safety concerns identified following review of ZINN and NEWBORN-1 clinical study reports as well as ARIOS adverse events (including congenital anomalies), neurodevelopment screening assessments (ASQ-3, CBCL/1.5-5, and MCHAT-R/F), and neurodevelopment referrals, from an ARIOS data cut on 15 June 2018, with 34 out of a total of 98 babies having already completed 24 months of safety follow-up. The IDMC also recommended that the neonatal follow-up be limited to 24 months of age given that the small number of enrolled subjects, in particular placebo subjects for comparison, would not yield meaningful results. Twenty-four months, in the IDMC collective opinion, would allow for detection of major neonatal adverse outcomes and safety signals and as such would be sufficient, especially considering that there will be no future development of retosiban.

Furthermore, 24-month outcomes are considered by the experts in the field to be appropriate for safety assessment (Marlow, 2014). [name], who is an IDMC member, in collaboration with regulatory agencies, has developed a manuscript (in press) that recommends that 24-month follow-up is appropriate for safety follow-up in this population.

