## 5. GENERAL CONSIDERATIONS FOR DATA ANALYSES AND DATA HANDLING CONVENTIONS

### 5.1. Primary Comparisons of Interest

The primary treatment groups are retosiban, placebo, and atosiban.

The primary comparisons between these treatment groups will be:

- Retosiban versus placebo
- Retosiban versus atosiban

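### SAP 10.4.1 shows retosiban only as one group pooled over two trials, so in the ARIOS Safety population at least 39 of its 49 infants were never randomised against placebo

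*SAP*

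**What the plan says.** Protocol 8.3.3.1 states: "The primary treatment groups are retosiban, placebo, and atosiban". SAP 5.1 repeats the two primary comparisons, the first being "Retosiban versus placebo" and the second retosiban against atosiban. Retosiban against the two comparators pooled is secondary (SAP 5.2).

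SAP 10.4.1 defines four display groups: NEWBORN-1 placebo, ZINN atosiban, the two comparators combined, and "Retosiban (Combined"). It defines no retosiban group by trial. The table shells are in a separate document (SAP 10.8) that was not available for this review.

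The pooling was deliberate. The Amendment 2 justification in protocol Appendix 1 says that "data from both 200719 and 200721 were to be pooled from all the babies exposed to retosiban and compared against placebo-exposed babies". The same text gives ARIOS enrolment as "6 placebo treated subjects from NB-1, 43 atosiban treated subjects from ZINN and 49 retosiban treated subjects from NEWBORN-1 and ZINN".

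**The concern.** Mothers were randomised to retosiban or placebo only within NEWBORN-1, and to retosiban or atosiban only within ZINN. Setting a retosiban group drawn mainly from ZINN beside a placebo group drawn wholly from NEWBORN-1 loses the protection of randomisation for most of the retosiban infants. Any difference in background outcome rates between the trials would then look like a difference between retosiban and placebo, in either direction.

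Two facts make comparability worth checking, though neither shows a bias.

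- Protocol 1.1.1 reports "18.9 days with retosiban (n=10) versus 11.1 days with placebo (n=13") in NEWBORN-1 and "32.51 days with retosiban (n=50) compared with 33.71 days with atosiban" in ZINN. The measures differ: the first is a mean time to delivery or treatment failure, the second an adjusted mean time to delivery.
- Uptake into ARIOS was 6 of 13 placebo infants (46%) against 43 of 47 atosiban infants (91%), taking the protocol 1.1.1 arm sizes as denominators.

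Baseline characteristics are also summarised by treatment group (SAP 6.3). Under 10.4.1 a reader could not see whether retosiban infants from the two trials differ in gestational age or birth weight.

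**Working it through.** **Inputs**

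- NEWBORN-1: retosiban 10, placebo 13. ZINN: retosiban 50, atosiban 47 (protocol 1.1.1).
- Enrolled: 23 in NEWBORN-1, 97 in ZINN (Protocol Summary, Rationale).
- One infant per mother: "Eligible subjects were aged 12 to 45 years with an uncomplicated singleton pregnancy and intact membranes in spontaneous preterm labor" (protocol 1.1.1).
- ARIOS: placebo 6, atosiban 43, retosiban 49, total 98, stated as 8% of a planned 1230 (protocol Appendix 1).

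**The plan's own figures reproduce.** 10 + 13 = 23; 50 + 47 = 97; 6 + 43 + 49 = 98; 900 + 330 = 1230; 98/1230 = 8.0%. The arm sizes therefore account for everyone enrolled.

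**Share of ARIOS retosiban infants from ZINN**

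- Lower bound: 49 − 10 = 39, and 39/49 = 79.6%.
- Upper bound: 48 (98.0%), because the protocol says the 49 came from both trials. Without relying on that wording it is 49.
- Share from NEWBORN-1, with the 48 bound: 1/49 = 2.0% to 10/49 = 20.4%.

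**What the display would show with no drug effect (ARIOS Safety, all enrolled infants with data).** Let k be the number of the 49 from NEWBORN-1 (1 to 10), and pN and pZ the background rates in NEWBORN-1 and ZINN.

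- Displayed retosiban rate = [k·pN + (49 − k)·pZ]/49
- Retosiban − placebo = [(49 − k)/49]·(pZ − pN), which is 79.6% to 98.0% of the trial difference
- Retosiban − atosiban = (k/49)·(pN − pZ), which is 2.0% to 20.4% of it

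The documents give no background rates, so the rates below are assumptions.

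| pN / pZ | Retosiban shown | Minus placebo (points) | Minus atosiban (points) |
|---|---|---|---|
| 20% / 8% | 8.2% to 10.4% | −11.8 to −9.6 | +0.2 to +2.4 |
| 10% / 10% | 10% | 0 | 0 |
| 10% / 20% | 18.0% to 19.8% | +8.0 to +9.8 | −2.0 to −0.2 |

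For example, at k = 10 in the first row: (10 × 0.20 + 39 × 0.08)/49 = 10.4%.

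**Chance for comparison.** With 0 events in 6 placebo infants, the exact 95% upper limit is 1 − 0.025^(1/6) = 45.9%. At a true rate of 10%, the placebo column shows no events with probability 0.9^6 = 53%.

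**Infant Safety (the primary population).** If the protocol 1.1.1 counts equal dosed mothers, 50 of 60 retosiban infants (83%) come from ZINN. The formulas above do not carry over to endpoints collected in ARIOS, because infants not enrolled stay in N (SAP 4 and 7.2) and missing data count as no event (SAP 10.6.2). With equal true rates of 10%, that rule alone would show placebo 6 × 0.10/13 = 4.6%, retosiban 49 × 0.10/60 = 8.2% and atosiban 43 × 0.10/47 = 9.1%. This is a separate distortion; it is not counted here, and by-trial columns would not cure it.

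**The case against.** The strongest reply is that this is a disclosed design choice. The protocol says retosiban was to be pooled, the SAP follows it, and the column is labelled as combined beside comparators labelled by trial. The output is counts and percentages, with no test or model. A reader who sees placebo at 20%, atosiban at 8% and retosiban at 8.2% to 10.4% has a cue that retosiban tracks the comparator from its main source trial. The rates are invented, and protocol 1.1.1 gives one eligibility description for both trials. Within NEWBORN-1 the split columns would hold 1 to 10 against 6 infants. The shells may already split by trial.

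Much of this stands. The pooling is intended and labelled, no inference is invalidated, bias is possible but not demonstrated, and the NEWBORN-1 columns add no precision. The adjacent comparator columns help only partly, because comparator and trial are completely confounded. Protocol 5.2, which keeps the parent-study treatment group and strata in the analysis, is compatible with by-trial columns but does not require them.

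The reply does not remove the main point. These tables are the study's principal output, and the study's stated goal is to give assurance about safety (protocol 1.2). A column of 49 beside a column of 6 hides the fact that at most 10 of the 49 share a randomisation with placebo. If the shells do split by trial, 10.4.1 should say so.

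**Conclusion.** The concern holds and should be fixed. In the ARIOS Safety population at least 39 of 49 retosiban infants (79.6%) come from a trial with no placebo arm, so the primary retosiban–placebo display is mainly cross-trial. For retosiban against atosiban the cross-trial share is at most 10/49 (20.4%).

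The bound rests on singleton pregnancies and on NEWBORN-1 mothers having received the treatment they were randomised to; no crossover is reported. Even the within-trial comparisons are protected by randomisation only apart from selection into ARIOS. The size and direction of any distortion are unknown, because they depend on a between-trial difference that the documents do not report. That retosiban appears only pooled is a statement about the SAP text, since the shells were not seen.

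**What to change.** Before unblinding:

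1. In SAP 10.4.1 add a NEWBORN-1 retosiban group and a ZINN retosiban group, each placed beside its randomised comparator. Use them in the baseline table (10.3) and the safety tables (10.5 to 10.10 and 20.5 to 20.10). Keep both combined groups.
2. Footnote these tables to say that pooled retosiban against placebo, and to a lesser degree against atosiban, includes non-randomised cross-trial data.

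The primary comparisons stay as written, and no model or stratified estimate is needed. Timing matters: SAP 1 fixes analysis decisions before database freeze, and SAP 8 rules out changes to the planned analyses after unblinding.

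The cost is four columns becoming six in 13 tables, plus a footnote, from data already held and with no protocol change. The downside is very small NEWBORN-1 cells, which make the limits of the placebo comparison visible without adding information. The main gain is the ZINN comparison, 39 to 48 retosiban infants against 43 atosiban infants, shown unmixed.

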### 10.4.2. Baseline Definition

Baseline characteristics and demographic data will be captured from the Phase III SPTL treatment studies and combined with child follow-up data for analyses. For all endpoints in ARIOS study, baseline value is not required for analysis.

### 10.4.3. Reporting Process & Standards

Reporting Process
Software

 
The currently supported versions of SAS software will be used to perform all data analyses, generate tables, figures, and listings.
 

Reporting Area
Analysis Datasets

 
Analysis datasets will be created according to ADaM implementation guide version 1.1.
 
RTF files will be generated.
 
All datasets are CDISC compliance.
 

Reporting Standards
General

 
The current GSK Integrated Data Standards Library (IDSL) will be applied for reporting, unless otherwise stated: 
 
4.03 to 4.23: General Principles
 
5.01 to 5.08: Principles Related to Data Listings
 
6.01 to 6.11: Principles Related to Summary Tables
 
 
 

Formats

 
For safety analyses, all data will be reported according to the actual treatment the mother received.
 
GSK IDSL Statistical Principles (5.03 & 6.06.3) for decimal places (DP's) will be adopted for
 

reporting of data based on the raw data collected.	

• Numeric data will be reported at the precision collected on the eCRF.

• The reported precision from non-eCRF sources will follow the IDSL statistical principles but may be adjusted to a clinically interpretable number of DP's.

	
Planned and Actual Time	

• Reporting for tables and formal statistical analyses :

• The impact of any major deviation from the planned assessment times and/or scheduled visit days on the analyses and interpretation of the results will be assessed as appropriate.

• Reporting for Data Listings:

• Planned and actual time relative to study drug dosing for mother will be shown in listings (Refer to IDSL Statistical Principle 5.05.1).

• Unscheduled or unplanned readings will be presented within the subject's listings.

• Visits outside the protocol defined time-windows (i.e. recorded as protocol deviations) will be included in listings but omitted from summaries and statistical analyses.

	
Unscheduled Visits	

• All unscheduled visits will be listed.

	
Descriptive Summary Statistics	
Continuous Data	Refer to IDSL Statistical Principle 6.06.1
Categorical Data	N, n, frequency, %
Graphical Displays	

• Refer to IDSL Statistical Principles 7.01 to 7.13.

	

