consent and medical release when the woman's acute episode of preterm labor has resolved and prior to discharge from the hospital for the treatment of preterm labor. The infant will be allowed to be consented into the study until the later date of either the date of discharge from the birth hospitalization or up to 9 months corrected age (to allow for the infant's 9-month Child Health Inventory [CHI] and ASQ-3 data collection) via follow-up contact from the research coordinating center-principal investigator (RCC-PI) to the parent/legal guardian. This follow-up contact and informed consent discussion may occur via telephone with signed consent and medical releases transmitted via mail or courier. Infants and children will be followed at prespecified intervals until they reach 24 months chronological age (see [Table 2](#)). This study does not require medical interventions or study visits to an investigational site. Instead, parents or legal guardians will be prompted at certain time points to complete developmental questionnaires and other data on their children's health status via an electronic device. Data collected during this follow-up study will be managed by a centralized RCC. Regionally based pediatricians will serve as study principal investigators (referred to as RCC-PIs) for this study. All communications the RCC-PI has with the parent/legal guardian or the child's HCP will occur remotely; there will be no clinic visits. An overview of the study design is shown in [Figure 1](#).

Figure 1 **Study Design**

EDD = estimated date of delivery; HCP = health care provider; RCC = research coordinating center; RCC-PI = research coordinating center-principal investigator; SPTL = spontaneous preterm labor.

Electronic data capture (eDC) tools and processes including electronic case report forms (eCRF) and electronic patient-reported outcome devices will allow entry of data, regardless of when it is obtained. If at any time the data suggest any developmental delay, the RCC-PI will refer the child to a specialist (if not already under the care of a specialist) for formal evaluation and additional assessments. The child's local primary care pediatric

provider will be asked to provide routinely available data on the child to the RCC. Additional contacts may occur at the discretion of the RCC personnel to complete the data collection.

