The M-CHAT-R/F will be completed for all infants at 18 and 24 months (corrected age) and the CBCL/1.5–5 will be completed for all infants at 24 months (corrected age) to assess the risk for other behavioral problems or autism spectrum disorder (ASD). If at any of these time points a child has an M-CHAT-R/F score that indicates further evaluation is required and/or a CBCL/1.5–5 score above the 97th percentile for a subset of prespecified questions, the child will be referred to a specialist for a formal assessment.

Protocol Amendment 2 has updated the total study duration to 24 months. Babies or infants that have passed the 24-month assessments after the amendment implementation are not required to continue further within the study, nor do they need to complete any subsequent study-related assessments. Following completion of the study, the neonates will continue their normal pediatric standard of care with their primary care pediatrician or health care provider.

The 24-month data will form the final study endpoint assessment timing; however, if data have been collected from a baby/infant after they have passed the 24-month endpoint, then this data will be included as a data listing within the clinical study report.

Data and genetic samples from the Phase III SPTL treatment studies may be used as part of a genetic analysis using data collected in this study, if relevant. No additional genetic samples are required.

Protocol waivers or exemptions are not allowed with the exception of immediate safety concerns. Therefore, adherence to the study design requirements, including those specified in the Time and Events Table (Table 2), are essential and required for study conduct. All specified completion windows for applicable questionnaires (CHI, ASQ-3, CBCL/1.5–5, M-CHAT-R/F, and productivity) are provided to help standardize the data and avoid overlap. Information captured outside of these windows will be collected and analyzed separately, and questionnaires completed outside the completion window will not be considered protocol deviations.

Supplementary study conduct information not mandated to be present in this protocol is provided in the accompanying Study Procedures Manual (SPM). The SPM will provide the site personnel with administrative and detailed technical information that does not impact subject safety.

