The M-CHAT-R/F is a parent-reported autism screening tool designed to identify children 16 to 30 months of age who should receive a more thorough assessment for possible early signs of ASD or developmental delay [Robins, 2014]. The M-CHAT-R/F consists of 20 questions that are answered with either “yes” or “no.” Total scores on the M-CHAT-R/F between 0 and 2 indicate a low risk, scores between 3 and 7 indicate a medium risk and triggers administration of the follow-up questionnaire, and scores between 8 and 20 indicate a high risk. In this study, infants with test scores that indicate that further evaluation is required (either after an initial medium-risk score and further follow-up or an initial high-risk score) will be considered to have possible signs of ASD or developmental delay and will be referred to a developmental specialist for a formal assessment.

The CBCL/1.5–5 is a widely used parent-completed questionnaire of the Achenbach System of Empirically Based Assessment (ASEBA). The ASEBA is based on carefully conducted empirical studies and is designed to assess, in a standardized format, behavioral problems and social competencies (Achenbach, 2001). The CBCL/1.5-5 includes approximately 100 items that describe specific kinds of behavioral, emotional, and social problems that characterize preschool children between the ages of 1.5 and 5 years. Scores on the full CBCL/1.5-5 between the 93rd and 97th percentile are in the borderline range and scores above the 97th percentile are in the significant range of clinical concern. In this study, infants with test scores above the 97th percentile for a subset of prespecified questions that relate to attention or hyperactivity problems syndrome or the American Psychiatric Association's Diagnostic and Statistical Manual (DSM)-oriented attention-deficit/hyperactivity disorder scale will be considered to have a behavior problem, which will trigger a referral to a developmental specialist for a formal assessment.

The completion window for the CBCL/1/5-5 and M-CHAT-R/F is +6 weeks at 18 months (M-CHAT-R/F only) and +12 weeks at 24 months; however, questionnaires completed outside the completion window will not be considered a protocol deviation.

For further details regarding the CBCL/1.5–5 and M-CHAT-R/F, refer to the SPM.

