## 2. SUMMARY OF KEY PROTOCOL INFORMATION

### 2.1. Changes to the Protocol Defined Statistical Analysis Plan

Due to early termination of the study, not all originally planned data analyses as outlined in the protocol will be performed. More details are given in Section 8.

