## **7.2.3. Neurodevelopment Assessment at 9, 18, and 24 months**

Neurodevelopment will be assessed by determining the proportions of infants diagnosed with developmental delays listed below at 9, 18, and 24 months of age, corrected for prematurity.

Endpoints related to Ages and Stages Questionnaire version 3 (ASQ-3) score and developmental evaluation described in Section 2.2 will be descriptively summarized at 9, 18, and 24 months by treatment group. For subjects with an ASQ-3 score in the black zone ( $\geq 2$  standard deviation [SD] below the mean) for any domain and referred for development evaluation, number of infants and percentage with Bayley Scales of Infant Development 3rd edition (BSID-III) and non-BSID-III results will be summarized. For subjects with an ASQ-3 score in the black zone for any domain, referred for development evaluation, but no assessment done, reason of no assessment done will be summarized. In addition to endpoints described in Section 2.2, number of infants and percentage with moderate or severe developmental delay using non BSID-III score will be summarized.

For BSID-III score, scaled scores for cognitive, receptive communication, expressive communication, fine motor, and gross motor will be derived from the subtest total raw scores and range from 1–19, with a mean of 10 and an SD of 3. Language composite scores will be derived from sums of receptive communication and expressive communication scaled scores. The composite score will be scaled to a metric with a mean of 100 and an SD of 15, and range from 40–160.

Endpoints related to Modified Checklist for Autism in Toddlers Revised with Follow-Up (M-CHAT-R/F) described in Section 2.2 will be descriptively summarized at 18, and 24 months by treatment group.

Endpoints related to Child Behavior Checklist for Ages 1.5 to 5 (CBCL/1.5-5) and cerebral palsy in Section 2.2 will be descriptively summarized at 24 months by treatment group.

Neurodevelopment assessment data will be presented in listings.

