## **8. DEVIATION OF PLANNED ANALYSES FROM PROTOCOL**

No changes will be made to the planned analyses after the breaking of the study blind.

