## 10.2. Appendix 2: Time and Events

Event	28 Days Post EDD	Months						
		2	6	9	12	15	18	21
Written informed consent 		←	→					
Baseline characteristics and demographic data	X 							
RCC confirms and updates contact information from the parent/legal guardian	X							
Parent/legal guardian completes CHI 		X	X	X	X	X	X	X
RCC-PI follows up with HCP and reviews medical or other records to confirm parent-reported outcomes								→
RCC-PI reviews CHI results and refers to birth-defect evaluator based on results								→
Parent/legal guardian completes productivity questionnaire 								
Parent/legal guardian completes ASQ-3 				X 			X 	X  →
RCC-PI reviews ASQ-3 results and refers for developmental evaluation based on results 								→
Parent/legal guardian completes M-CHAT-R/F 							X	X
Parent/legal guardian completes CBCL/1.5–5 								X
RCC-PI refers child to specialist for cerebral palsy assessment (if required) 								X

ASQ-3 = Ages and Stages Questionnaire-3; CBCL/1.5–5 = Child Behavior Checklist for ages 1.5 to 5; CHI = Child Health Inventory; EDD = estimated date of delivery; HCP = health care provider; M-CHAT-R/F = Modified Checklist for Autism in Toddlers-Revised with Follow-Up; RCC = research coordinating center; RCC-PI = research coordinating center-principal investigator.

Note: All specified completion windows for applicable questionnaires (CHI, ASQ-3, CBCL/1.5–5, M-CHAT-R/F, and productivity) are provided to help standardize the data and avoid overlap. Information captured outside of these windows will be collected and analyzed separately, and questionnaires completed outside the completion window will not be considered protocol deviations.

1. Collected at the start of the Phase III spontaneous preterm labor (SPTL) treatment studies until the later date of either the date of discharge from the birth hospitalization or up to 9 months corrected age (to allow for the infant's 9-month CHI and ASQ-3 data collection).
2. Captured in Phase III SPTL treatment studies and combined with child follow-up data for analyses.
3. A positive response by the parent/legal guardian may trigger follow-up with the relevant HCP and/or medical record review for confirmation or more details on the condition or hospitalization. At each time point, the completion window of the CHI is +6 weeks.

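### SAP 10.4.3 treats out-of-window questionnaires as deviations and only lists them; the protocol and SAP Appendix 2 say they are not deviations and are analysed separately

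*SAP*

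**What the plan says.** SAP 10.4.3, under planned and actual time, gives this rule: "Visits outside the protocol defined time-windows (i.e. recorded as protocol deviations) will be included in listings but omitted from summaries and statistical analyses". A companion line says the impact of major timing deviations will be assessed as appropriate, without naming an analysis.

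The rest of the plan says otherwise:

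- Protocol 3.1, the note to protocol Table 2 and the note in SAP Appendix 2 all carry the same handling rule: "Information captured outside of these windows will be collected and analyzed separately".
- The same notes settle deviation status: "questionnaires completed outside the completion window will not be considered protocol deviations". Protocol 6.2.5 repeats it for the ASQ-3 and for the M-CHAT-R/F and CBCL/1.5-5: "questionnaires completed outside the completion window will not be considered a protocol deviation". Sections 6.2.1.1 (CHI) and 6.3.1 (productivity questionnaire) do the same.
- Protocol 3.1 says of the study's contacts that "there will be no clinic visits". The windows it defines are completion windows for questionnaires.
- SAP 7.2.3 says the ASQ-3 and developmental evaluation endpoints "will be descriptively summarized at 9, 18, and 24 months by treatment group". Protocol Table 1 places these among the primary objectives' endpoints.
- SAP 2.1 says that "not all originally planned data analyses as outlined in the protocol will be performed" and refers to Section 8 for details. Section 8 contains one sentence: "No changes will be made to the planned analyses after the breaking of the study blind".

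**The concern.** On deviation status the two rules cannot both be followed. On handling, SAP 10.4.3 provides a listing and nothing more, where the protocol and Appendix 2 provide a separate analysis.

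The results affected are completed parent screens that feed primary neurodevelopment endpoints, and chronic conditions that first come to light on an out-of-window CHI. Under 10.4.3 as written, a reader of the tables could not see by treatment group how many forms fell outside the window or how many of those were abnormal. SAP Appendix 1 says no deviation summary will be presented, so the information would not surface there either.

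Such forms are foreseeable. The Month 9 ASQ-3 window and the CHI windows run forward only, and protocol 7.1.1 allows assessments to be collected after a case lost to follow-up is re-opened.

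Two further gaps follow. SAP 7.2.3 ties its BSID-III rows to children with a black-zone ASQ-3 who were referred, and does not say whether those rows survive when that ASQ-3 was out of window. SAP 10.6.2 assumes that events did not occur where safety or neurodevelopment data are missing, and does not say how a completed but omitted form is classed.

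**Working it through.** The plan states no figure on this point, so the first step is a comparison of texts.

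**1. The two rules side by side**

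| Question | SAP 10.4.3 | Protocol 3.1, Table 2 note, SAP Appendix 2 |
|---|---|---|
| Is an out-of-window form a deviation? | Yes | No |
| Does it enter the main by-group rows? | No | No, because it is handled separately |
| Is there a separate analysis? | No, listing only | Yes, form not specified |

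The conflict is in the first and third rows. The second row is common ground.

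**2. What the SAP rule acts on.** The windows are CHI +6 weeks; ASQ-3 +30 days at Month 9 and ±30 days at Months 18 and 24; M-CHAT-R/F +6 weeks at 18 months; M-CHAT-R/F and CBCL/1.5-5 +12 weeks at 24 months; productivity questionnaire +2 weeks. The last is only listed (SAP 7.2.6), so no table depends on it. The others feed Tables 10.6/20.6, 10.7/20.7 and 10.8/20.8. Through the 24-month BSID-III results, Tables 10.9/20.9 may also be affected.

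**3. Is it a declared departure?** No. SAP 2.1 points to Section 8, and Section 8 lists no change.

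**4. Weight of one form if full group N is the divisor.** The move is 1/N. Enrolled counts are in protocol Appendix 1, in the justification for Amendment 2.

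- Placebo: 1/6 = 16.7 points
- Atosiban: 1/43 = 2.3 points
- Retosiban: 1/49 = 2.0 points
- All comparators: 6 + 43 = 49, so 1/49 = 2.0 points

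For the Infant Safety tables, taking the group sizes in protocol 1.1.1 as N (placebo 13, atosiban 47, retosiban 10 + 50 = 60, comparators 13 + 47 = 60), the moves are 7.7, 2.1, 1.7 and 1.7 points. These are approximate, because SAP Section 4 groups infants by actual treatment.

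**5. Effect of the divisor.** Let p be the true abnormal proportion and f the out-of-window share. The documents give neither, so both are assumed. If timing is unrelated to outcome:

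- Full N as divisor: p(1 − f). With p = 20% and f = 20%, 0.20 × 0.80 = 16%. With f = 10% in one group and 30% in another, 0.20 × 0.90 = 18% against 0.20 × 0.70 = 14%, an artificial difference of 4 points.
- Children with an in-window form as divisor: p(1 − f)/(1 − f) = p = 20% in every case.

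If out-of-window completion is assumed twice as common in abnormal children, again with p = 20%:

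- 20% against 10%: in-window divisor 0.16/(0.16 + 0.72) = 18.2%; full N 0.20 × 0.80 = 16%.
- 40% against 20%: in-window divisor 0.12/(0.12 + 0.64) = 15.8%; full N 0.20 × 0.60 = 12%.

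The 18.2% and 15.8% come from windowing itself and would arise under the protocol's rule too. The separate out-of-window rows would make them visible.

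**6. Missing data.** SAP 10.6.2 describes missing data as requested data not provided, leaving blank fields. A completed late form is not blank, so the better reading is that it is not missing. The section does not say so.

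**The case against.** The strongest reply is that the main tables come out the same whichever rule is used, because separate analysis also keeps out-of-window forms out of the main rows. That stands. A reader might infer that 10.4.3 removes from the main proportions results that the protocol would have counted there; the documents do not support it.

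A second tempting inference starts from a narrow reading, in which 10.4.3 acts only on forms actually recorded as deviations. Questionnaires never are, so the forms would seem to be pooled into the main rows. No text provides for pooling, and Appendix 2 would still require separation.

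Third, the point moves might be taken as a measured bias. They are not. SAP 7.2 says tables include N, not that N is the divisor, and no out-of-window rate is given. Nor does 10.6.2 by its terms turn a completed form into a non-event; it only leaves room for that reading.

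Fourth, it can be argued that a listing satisfies separate analysis, and that the shells may contain the summary. No titled table in SAP Appendix 8 provides one, but the shells are a separate document, and Tables 10.11/20.11 are numbered without a title. It cannot be said that the summary is absent from the full set of outputs. Against the listing argument, neither document says a listing is enough, and 10.4.3 sets listing apart from summary and analysis.

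Finally, the study is descriptive and tests no hypothesis, so no inference is invalidated and the individual data remain in listings. That limits the weight of the point but leaves the conflict on deviation status untouched.

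**Conclusion.** The concern holds as an undeclared conflict between SAP 10.4.3 and both the protocol and the SAP's own Appendix 2. In practical terms, 10.4.3 followed literally loses the by-group account of completed out-of-window screens and CHI reports, while the divisor and the missing-data status of those forms are left unstated. It does not show that the main-row proportions differ between the two rules.

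The size cannot be estimated from the documents. The one-form moves in step 4 depend on full N as divisor, and the percentages in step 5 depend on assumed rates. With 6 placebo infants enrolled, even one form deserves a clear rule. The SAP should be corrected before database freeze, since SAP Section 1 requires analysis decisions to be made by then.

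**What to change.** - **SAP 10.4.3:** delete the parenthesis that equates out-of-window visits with recorded deviations, and replace the omission rule with the Appendix 2 rule.
- **Tables 10.7/20.7 and 10.8/20.8:** keep in-window forms in the main rows, with children who have an in-window form as the divisor. Add, by treatment group and time point, the number of out-of-window forms and the number abnormal.
- **SAP 10.6.2:** state that a completed out-of-window form is not missing and is not counted as a non-event.
- **Tables 10.6/20.6, 10.7/20.7 and 10.9/20.9:** state that the timing of the triggering questionnaire does not remove referrals, BSID-III results or medically confirmed conditions.

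The choice of divisor and the exact content of the added rows are recommendations of this review; the protocol asks only for separate analysis. The cost is SAP wording and a few table rows, with no protocol amendment. The downside is slightly longer tables and a wider spread of age at assessment in the out-of-window rows.
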